## CONTRACEPTION GUIDANCE FOR MALE PATIENTS WITH PARTNER(S) OF CHILDBEARING POTENTIAL

For Arm A (bempegaldesleukin plus pembrolizumab): male patients with female partners of childbearing potential are eligible to participate if they agree to the following during the treatment and until the end of relevant systemic exposure.

- Inform any and all partner(s) of their participation in a clinical drug study and the need to comply with contraception instructions as directed by the Investigator.
- Male patients are required to use a condom for study duration and until end of relevant systemic exposure defined as 3 months after the last dose of bempegaldesleukin.
- Female partners of males participating in the study to consider use of effective methods of contraception until the end of relevant systemic exposure, defined as 3 months after the last dose of bempegaldesleukin in the male patient.
- Male patients with a pregnant or breastfeeding partner must agree to remain abstinent from penile vaginal intercourse or use a male condom during each episode of penile penetration during the treatment and until 3 months after the last dose of bempegaldesleukin.
- Refrain from donating sperm for the duration of the study treatment and until 3 months after the last dose of bempegaldesleukin.

For Arm B (pembrolizumab monotherapy): For male patients receiving pembrolizumab monotherapy, there are no contraception requirements.

## COLLECTION OF PREGNANCY INFORMATION

Guidance for collection of Pregnancy Information is provided in Section [10.16](#).

## APPENDIX 6: CYTOKINE-RELEASE SYNDROME (CRS) MANAGEMENT MEASURES/ALGORITHM FOR PATIENTS IN ARM A RECEIVING BEMPEGALDESLEUKIN

The following treatment management guideline is provided for general guidance for patients in Arm A receiving bempegaldesleukin. Cytokine-release syndrome (CRS) is a diagnosis of exclusion. This guideline should not substitute for a more individualized, tailored approach to managing a patient experiencing CRS.

As a general principle, differential diagnoses should be diligently evaluated according to standard medical practice. Non-inflammatory etiologies should be considered and appropriately treated.
 
For patients with suspected CRS:
 
 
• For Grade 1 or Grade 2 events, implement supportive care, including management of isolated symptoms based on institutional practices
 
• Consider admitting the patient for monitoring and to provide supportive care, including management of isolated symptoms based on institutional practices and protocol management guideline (eg, hydration management guidelines in Section 6.2.3.2).
 
• For patients with a persistent or worsening clinical condition after initial treatment of CRS, re-evaluate for other contributing conditions. It is particularly important to reassess the patient for coexisting infections, cardiac, pulmonary, thromboembolic, and other complications.
 
		
Grading Assessment per CTCAE Version 5.0		Treatment Measures Recommended
CRS Grade 3	
 
• Hypotension managed with 1 pressor
 
• Hypoxia requiring > 40% O2
 
	
 
• Vasopressin administration should be considered if the hypotensive event is refractory to > 3 L of fluid resuscitation.
 
• Oxygen therapy (nasal canula, non-invasive positive pressure ventilation, etc.) for respiratory symptoms with consideration of intubation for a patient with severe respiratory manifestations.
 

CRS Grade 4	
 
• Life-threatening consequences
 
• Pressor or ventilatory support indicated
 
	
 
• Supportive care for renal, hepatic and other organ function deteriorations.
 
• Steroid therapy should be considered (eg, hydrocortisone 100 mg every 8 hours, dexamethasone 10 mg up to 4 times daily, 1 to 2 mg/kg/day methylprednisone IV or PO equivalent).
 
• High-dose steroid (eg, solumedrol 2 mg/kg up to 1 gram daily for 3 days) may be considered for severe CRS that failed to respond after repetitive steroid treatments.
 
• For severe CRS cases that require simultaneously aggressive management of hypotension, oxygenation and cardiac telemetry, consult Intensivist for ICU evaluation.
 

Abbreviations: ICU = intensive care unit; O2 = oxygen; PO = by mouth

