### 6.5.1.2 Bempegaldesleukin Dose Delay and Reduction Criteria

Dose delays and one dose reduction are permitted for bempegaldesleukin. Bempegaldesleukin may be delayed or reduced to 0.003 mg/kg based on observed drug-related toxicities. Medical Monitor consultation is required for dose reduction. For patients who have a dose reduction to 0.003 mg/kg: if the toxicity requiring dose reduction has resolved, bempegaldesleukin 0.006 mg/kg may be reinstated after a careful risk assessment.

Bempegaldesleukin may be delayed or reduced for the following reasons:

- For infusion reactions, refer to Section 6.5.2.1.1.
- For irAEs, refer to Section 6.5.2.1.2.
- Grade  $\geq 2$  creatinine increase:
  - For patients who must delay study treatment due to Grade  $\geq 2$  creatinine increase due to a non-inflammatory cause, delay retreatment with study drug for approximately 3 to 5 days. After the dosing delay, the patient may resume study drug when serum creatinine has returned to Grade  $\leq 1$ , as assessed within 24 hours prior to redosing (or as soon as locally feasible, except where permanent discontinuation of study drug is required [see Section 6.5.1.3]).
- Grade  $\geq 3$  toxicity at least possibly related to bempegaldesleukin: bempegaldesleukin must be delayed until resolution to Grade 1 or baseline (unless otherwise requiring permanent discontinuation per Section 6.5.1.3), patients with the following laboratory values can continue study drug:
  - Grade  $\geq 3$  lymphopenia
  - Grade  $\geq 3$  asymptomatic amylase or lipase elevation
- Patient has acute infection (eg, fever, upper or lower respiratory tract infection) requiring systemic antibiotic therapy. Patient may resume study treatment once free of signs or symptoms for 72 hours after completion of antibiotic therapy.
- For eosinophilia, refer to Section 6.5.1.1.4.
- Any AE, laboratory abnormality, or intercurrent illness which, in the judgment of the Investigator, warrants delaying the dose of study medication.

Bempegaldesleukin dosing may resume at the same bempegaldesleukin dose or at the lower bempegaldesleukin dose level when toxicity resolves to Grade  $\leq 1$  or returns to baseline, except for instances where the potential recurrence of the event poses an undue risk for the patient.

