### 6.5.1.3 Bempegaldesleukin Discontinuation Criteria

For toxicities requiring discontinuation of treatment with bempegaldesleukin, pembrolizumab alone may continue as a monotherapy if the toxicity is considered by the Investigator to be not related to pembrolizumab.

For CVA events and suspected TIA events, follow the criteria described below (additional details are provided in the CVA management algorithm in [Appendix 2](#)).

Bempegaldesleukin treatment should be permanently discontinued for the following:

- For infusion reactions, in accordance with the criteria in Section [6.5.2.1.1](#).
- For irAEs, in accordance with the criteria in Section [6.5.2.1.2](#).
- For any Grade 4 drug-related AE or clinically significant laboratory abnormality, with the exception of the following events, which do not require discontinuation:
  - Grade 4 neutropenia  $\leq$  7 days.
  - Grade 4 lymphopenia or leukopenia  $\leq$  14 days in duration.
  - Isolated Grade 4 amylase or lipase abnormalities that are not associated with symptoms or clinical manifestations of pancreatitis and decrease to Grade  $<$  4 or return to baseline within 7 days.
  - Isolated Grade 4 electrolyte imbalances/abnormalities that are not associated with clinical sequelae and are corrected with supplementation/appropriate management within 72 hours of their onset.
- Any AE, laboratory abnormality, or intercurrent illness that, in the judgment of the Investigator, presents a substantial clinical risk to the patient with continued treatment.
- Any new CVA event confirmed by imaging (diffusion-weighted imaging [DWI] MRI preferred unless otherwise contraindicated) regardless of neurological symptoms (eg, cryptogenic CVA) and for a suspected TIA event without clear alternative etiology (see [Appendix 2](#)).

Tumor assessments should continue as per protocol even if dosing is delayed, and patients must otherwise meet the criteria for continued treatment at the time re-initiation of study therapy is considered.

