
Grades 3 or 4
 
Grade 3: Prolonged (ie, not rapidly responsive to symptomatic medication and/or brief interruption of infusion); recurrence of symptoms following initial improvement; hospitalization indicated for other clinical sequelae (eg, renal impairment, pulmonary infiltrates)
 
Grade 4: Life-threatening; pressor or ventilatory support indicated
	
Stop Infusion.
 
Additional appropriate medical therapy may include but is not limited to:
 
 
• Epinephrine**
 
• IV fluids
 
• Antihistamines
 
• NSAIDs
 
• Acetaminophen
 
• Narcotics
 
• Oxygen
 
• Pressors
 
• Corticosteroids
 
 
Increase monitoring of vital signs as medically indicated until the patient is deemed medically stable in the opinion of the Investigator.
 
Hospitalization may be indicated.
 
** In cases of anaphylaxis, epinephrine should be used immediately.
 
Patient is permanently discontinued from further study drug intervention.
	
No subsequent dosing

Abbreviations: CTCAE = Common Terminology Criteria for Adverse Events; IV = intravenous; NCI = National Cancer Institute; NSAIDs = nonsteroidal anti-inflammatory drugs; PO = by mouth

Appropriate resuscitation equipment should be available at the bedside and a physician readily available during the period of drug administration.

For further information, please refer to the Common Terminology Criteria for Adverse Events v5.0 (CTCAE) at <http://ctep.cancer.gov>

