## 10.3 Grading of AEs

The severity of an event and the seriousness are not to be considered synonymous. The severity is grading the intensity of an event. The seriousness of event is based on the patient/event outcome or action criteria. All AEs will be assessed for severity using the National Cancer Institute Common Terminology Criteria for Adverse Events (NCI-CTCAE) version 5.0 guidelines. If a particular AE is not listed in the NCI-CTCAE, the following criteria will be used:

- Grade 1 = Mild (event results in mild or transient discomfort, not requiring or needing only minimal intervention or treatment; does not limit or interfere with daily activities [eg, insomnia, mild headache]).

- Grade 2 = Moderate (event is sufficiently discomforting so as to limit or interfere with daily activities; may require interventional treatment [eg, fever requiring antipyretic medication]).
- Grade 3 = Severe (event results in significant symptoms that prevent normal daily activities; may require hospitalization or invasive intervention).
- Grade 4 = Life threatening or disabling.
- Grade 5 = Death.

AEs will be reported with an individual start and stop date for each level of severity.

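### Appendix 6 lets cytokine-release syndrome managed with one pressor fit both Grade 3 and Grade 4, and the grade determines whether the mandatory stop of bempegaldesleukin applies

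*Protocol*

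**What the plan says.** Protocol Appendix 6 is the management guide for CRS in Arm A. Its grading column is headed "Grading Assessment per CTCAE Version 5.0". Grade 3 has two bullets: "Hypotension managed with 1 pressor", and hypoxia above a stated oxygen requirement. Grade 4 also has two: "Life-threatening consequences" and "Pressor or ventilatory support indicated". No AND or OR is stated between the bullets of either row. The appendix describes itself as general guidance and contains no dosing rule.

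The dosing rules are elsewhere:

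- Section 6.5.1.2 covers Grade 3 or higher "toxicity at least possibly related to bempegaldesleukin: bempegaldesleukin must be delayed until resolution to Grade 1 or baseline", unless Section 6.5.1.3 requires a permanent stop. Dosing may then resume at the same or the lower dose level, except where recurrence would pose undue risk.
- Section 6.5.1.3 requires permanent discontinuation "For any Grade 4 drug-related AE or clinically significant laboratory abnormality, with the exception of the following events, which do not require discontinuation". The exceptions are certain neutropenia, lymphopenia or leukopenia, amylase or lipase, and electrolyte findings. CRS is not among them.
- Section 6.5.1.1.3 refers CRS to Appendix 6, requires the Investigator to contact the Sponsor for suspected serious CRS of Grade 3 or higher, and notes that the symptoms can also be seen in infusion reactions.
- Table 5 in Section 6.5.2.1.1 defines a Grade 4 infusion reaction as "Life-threatening; pressor or ventilatory support indicated" and ends study drug for Grades 3 and 4 alike.

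**The concern.** A grading table attached to a dosing rule should put each event in one row. Here the Grade 3 row names one pressor and the Grade 4 row names pressor support without a number. A site treating a patient whose only qualifying feature is hypotension on a single pressor can support either grade from the text.

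What is at stake is whether a mandatory rule applies. If the event is related to bempegaldesleukin and graded 4, the protocol requires a permanent stop. If it is graded 3, the protocol requires a delay and allows re-exposure after recovery. The protocol lists hypotension and cytokine-related toxicities among the identified risks of bempegaldesleukin (Section 2.2.1), so the ambiguity falls on a toxicity the trial expects to manage.

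**Working it through.** No stated figure is to be reproduced; the check is of the text.

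**Step 1: do the rows overlap?** Take drug-related CRS with hypotension on exactly one pressor and no other qualifying feature.

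| Reading of the two Grade 4 bullets | Fits Grade 3? | Fits Grade 4? |
|---|---|---|
| Alternatives (either is enough) | Yes | Yes |
| Both required | Yes | No, without life-threatening consequences |

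The table does not say which reading is meant. The two Grade 3 bullets, hypotension and hypoxia, read naturally as alternatives, which favours the first line. A convention that the higher grade wins would not rescue that line: every one-pressor case would then be Grade 4, and the Grade 3 hypotension bullet could never be used.

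**Step 2: what follows from each grade?**

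| Handled as | Grade 3 | Grade 4 |
|---|---|---|
| Related toxicity, Sections 6.5.1.2 and 6.5.1.3 | Delay, possible resumption | Permanent discontinuation |
| Other immune-related event, Table 6 | Withhold or discontinue, depending on the event (recurrent Grade 3: discontinue) | Permanent discontinuation |
| Infusion reaction, Table 5 | Permanent discontinuation | Permanent discontinuation |

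In the first two rows the grade can change the required action. In the third it does not, so the choice of table matters as well. The text accompanying Tables 5 and 6 allows the other drug to continue alone if the toxicity is judged unrelated to it.

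**Step 3: is there a tie-breaker?** The clause in Section 6.5.1.2 that yields to Section 6.5.1.3 settles which section prevails once an event is Grade 4. It does not settle whether the event is Grade 4. The Sponsor-contact requirement starts at Grade 3, so it does not separate the two grades. Section 10.3 states "All AEs will be assessed for severity using the National Cancer Institute Common Terminology Criteria for Adverse Events" version 5.0, the same source Appendix 6 names, but the scale's text is not in the documents.

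**Step 4: can the number of patients be derived?** Section 2.1.3.2.2 gives Grade 3 or higher hypotension in 488 patients on bempegaldesleukin plus nivolumab: 3.5% from any cause and 2.7% treatment-related. Applied to the planned 250 patients in Arm A, assuming the rates carry over:

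- 0.035 × 250 = 8.75
- 0.027 × 250 = 6.75

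These are hypotension counts, not CRS on a pressor. In the monotherapy study, Grade 3 hypotension was rapidly reversed with intravenous fluids (Section 2.1.3.2.1), so Grade 3 hypotension does not imply pressor use. The documents give no rate of CRS on one pressor.

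**The case against.** The strongest answer is that grade does not control re-dosing. Section 6.5.1.2 bars resumption where recurrence would be an undue risk, Section 6.5.1.3 lets the Investigator stop at any grade for substantial clinical risk, and the Sponsor must be contacted for serious CRS under either grade. Appendix 6 is general guidance, and a site can consult CTCAE version 5.0 directly. This stands in part. A reader might infer that the row a site picks by itself decides whether a patient is re-exposed; the documents do not support that. Discretion to stop still does not tell a site whether it must stop.

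A second answer is that both Grade 4 bullets may be required, which would remove the overlap for a one-pressor case without life-threatening consequences. That is possible, but the table would have to say so.

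Three stronger readings are also unsupported:

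- **That one row is wrong against CTCAE, or that Table 5 wording was misplaced in Appendix 6.** The scale is not in the documents, and Table 5 grades a different event, so a different threshold there is not itself a contradiction.
- **That Grade 3 and Grade 4 counts seen by the Data Monitoring Committee are unreliable.** The text shows only that a one-pressor case could be counted in either grade.
- **That the CRS case in the monotherapy study indicates how often this would arise.** It is one patient at 0.012 mg/kg, twice this trial's starting dose of 0.006 mg/kg. That patient then tolerated two further cycles at 0.006 mg/kg.

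**Conclusion.** The point holds as a wording inconsistency with a dosing consequence. With the Grade 4 bullets read as alternatives, CRS managed with one pressor fits both grades, and nothing else in the documents resolves it. For an event judged drug-related and handled as CRS, the grade determines whether the mandatory permanent stop applies or delay with possible resumption; it is not the only determinant of what happens to the patient.

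The conclusion rests on three conditions: the bullets are alternatives, the event is judged related to bempegaldesleukin, and it is not handled as an infusion reaction under Table 5.

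The number of affected patients cannot be derived. SAP Section 2.0 reports one patient enrolled and treated, with listings only, so the effect on this trial's results is minimal. The correction matters chiefly if the protocol text is reused.

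**What to change.** Reconcile the Grade 3 and Grade 4 rows of Appendix 6 so that their pressor criteria are mutually exclusive, and state whether the bullets within each row are alternatives or jointly required. Add a cross-reference from the resulting grade to Sections 6.5.1.2 and 6.5.1.3. State whether Appendix 6 or Table 5 governs when a reaction could be graded under either. Which grade and which dosing action should apply is for the sponsor to decide.

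The cost is an edit to two table cells and short cross-references, made through an amendment or in any later protocol that reuses the text. No new data are needed.

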1.0 INTRODUCTION

This document provides an update of the statistical analysis plan for data captured in Nektar Therapeutics Protocol 20-214-36 “A Phase2/3, Randomized, Open-label Study to Compare Bempegaldesleukin Combined with Pembrolizumab Versus Pembrolizumab Alone in First-Line Treatment of Patients with Metastatic or Recurrent Head and Neck Squamous-Cell Carcinoma with PD-L1 Expressing Tumors (PROPEL-36)” Original version dated 14 June 2021.

On March 14, 2022, Nektar Therapeutics reported negative efficacy results in their Phase 3 melanoma study. On April 14th, 2022, negative topline results from both PIVOT-9 (renal cell carcinoma) and PIVOT-10 (urothelial) studies were reported. Based on three negative studies, Nektar Therapeutics made the decision to discontinue the bempegaldesleukin in combination with nivolumab program. As part of this decision, SFJ Pharmaceuticals, Inc. and Nektar Therapeutics, in consultation with the study Independent Data Monitoring Committee, have decided to discontinue the PROPEL-36 trial.

2.0 ANALYSIS PLAN

One patient was enrolled and treated in this study. No summary will be produced, instead, individual patient level listings with the following data will be provided.

Patient disposition, demographics and baseline characteristics will be described using listings of individual patient data. Patient demographics and baseline characteristics will include age, gender, ethnicity, race, geographic region, disease stage, primary tumor location, and disease status (metastatic vs recurrent only), PD-L1 tumor expression (CPS \geq 20 vs CPS 1-19), and HPV status (positive or negative), as applicable.

Prior and concomitant medications and therapies will be described using listings of individual patient data.

Adverse events (AEs) collected in the study will be described using AE listings including AE start and end dates, grade, relatedness to study drug, action taken and AE outcome. Adverse events will be coded by system organ class (SOC) and preferred term (PT) using MedDRA version 24.0. Adverse event severity will be based on National Cancer Institute Common Terminology Criteria for Adverse Events (NCI CTCAE) Grade (version 5.0). An AE is considered as related to treatment if it is related to any study drug; an AE with a missing relationship will be counted as related to study drug. An AE is considered as leading to treatment discontinuation if it is leading to discontinuation of any study drug. An AE is considered as leading to death if the severity grade is 5 or the outcome is fatal.
